## 8.2 Time period for reporting adverse events and serious adverse events

---

For each patient the standard time period for collecting and recording AE and SAEs will begin at the start of study treatment and will continue for half a year subsequent to study drug administration (until the end-of-study visit). We will proactively follow up all AEs and SAEs for each patient during the course of the study; events will be followed up to resolution, unless the event is considered to be unlikely to resolve due to the underlying disease. Every effort should be made to obtain a resolution for all events, even if the events continue after discontinuation/study completion. Mandatory reporting of new AEs ends after the end-of-study visit 6 months after study drug infusion.

## 8.3 Recording of adverse events

---

If the patient has experienced adverse event(s), the investigator will record the following information in the CRF:

The **nature of the event(s)** will be described by the investigator in precise standard medical terminology (i.e. not necessarily the exact words used by the patient).

The **duration of the event** will be described in terms of event onset date and event ended date.

The **intensity** of the adverse event will be categorised as mild / moderate / severe / life-threatening / death according to Common Terminology Criteria for Adverse Events version 4.0:

- Mild: asymptomatic or mild symptoms; clinical or diagnostic observations only; intervention not indicated;
- Moderate; minimal, local or non-invasive intervention indicated; limiting age-appropriate instrumental activities of daily life;
- Severe: Severe or medically significant but not immediately life-threatening; hospitalisation or prolongation of hospitalisation indicated; disabling; limiting self-care activities of daily life;
- Life-threatening consequences: urgent intervention indicated.

The **causal relationship** of the event to the study medication will be assessed as one of the following:

- Unrelated: There is not a temporal relationship to investigational product administration (too early, or late, or investigational product not taken), or there is a reasonable causal relationship between non-investigational product, concurrent disease, or circumstance and the AE.
- Unlikely: There is a temporal relationship to investigational product administration, but there is not a reasonable causal relationship between the investigational product and the AE.
- Possible: There is reasonable causal relationship between the investigational product and the AE. Dechallenge information is lacking or unclear.
- Probable: There is a reasonable causal relationship between the investigational product and the AE. The event responds to dechallenge. Rechallenge is not required.
- Definite: There is a reasonable causal relationship between the investigational product and the AE.

Action taken: **Which investigations/medical procedures/treatments that are initiated as a result of the adverse event.**

The **outcome** of the adverse event – whether the event is resolved or still ongoing.

It is important to distinguish between seriousness and severity of AEs. Severity is a measure of intensity whereas seriousness is defined by the criteria in Section 8.1. An AE of severe intensity need not necessarily be considered serious. For example, nausea that persists for several hours may be considered severe nausea, but is not an SAE. On the other hand, a stroke that results in only a limited degree of disability may be considered a mild stroke, but would be an SAE.

## 8.4 Reporting procedure

---

### 8.4.1 Adverse events, adverse events of special interest and serious adverse events

---

All adverse events and serious adverse events that should be reported as defined in section 8.1.1 will be recorded in the patient's CRF. SAEs must be reported by the investigator to the sponsor, Oslo University Hospital, within 24 hours after the site has gained knowledge of the SAE. The Serious Adverse Event Report Form must be completed, documented in the CRF, signed and sent to [name]. The initial report shall promptly be followed by detailed, written reports if necessary. The initial and follow-up reports shall identify the trial subjects by unique trial code numbers assigned to the latter. The sponsor keeps detailed records of all SAEs reported by the investigators and performs an evaluation with respect to seriousness, causality and expectedness. Adverse events of specific interest and any SAEs as defined above must be reported to the study drug manufacturer (Pharmacosmos®) within 24 hours after the site has gained knowledge of the event in question.

### 8.4.2 Suspected unexpected serious adverse reactions

---

SUSARs will be reported to the Norwegian Medicines Agency and the Ethics Committee according to national regulation. The following timelines should be followed:

The sponsor will ensure that all relevant information about suspected serious unexpected adverse reactions that are fatal or life-threatening is recorded and reported as soon as possible to the Norwegian Medicines Agency and the Regional Committee for Medical and Health Research Ethics in any case no later than seven (7) days after knowledge by the sponsor of such a case, and that relevant follow-up information is subsequently communicated within an additional eight (8) days. The sponsor shall ensure that suspected adverse reactions that are serious and unexpected are reported to the Norwegian Medicines Agency and to the Regional Committee for Medical and Health Research Ethics within 15 days of the sponsor after knowledge of the event. The sponsor shall inform all investigators of the trial substance in question of suspected adverse reactions that are serious and unexpected. An account of any interruption in treatment or any breaking of the treatment code, the investigator's assessment of the causal relationship, and consequences for further testing shall accompany the notification of suspected adverse reactions pursuant to the first and second paragraphs.

The Norwegian Medicines Agency may require that individual reports of adverse events described in collective reports should also be submitted. The sponsor shall keep detailed records of all adverse events that are reported to him by the investigator. The records shall be submitted to the Norwegian Medicines Agency on request.

### 8.4.3 Annual safety report

---

Once a year throughout the clinical trial, the sponsor will provide the Norwegian Medicines Agency with an annual safety report. The format will comply with national requirements.

### 8.4.4 Clinical study report

---

The adverse events and serious adverse events occurring during the study will be discussed in the safety evaluation part of the Clinical Study Report.

## 8.5 Procedures in case of emergency

---

The investigator is responsible for assuring that there are procedures and expertise available to cope with emergencies during the study.

Provide information regarding code break, if applicable (see also section 10.2.3).

## 8.6 Safety monitoring

---

An experienced specialist in internal medicine will be appointed to assess trial safety. This clinician will receive reports summarising patient recruitment and the number of AEs / SAEs after the first 20 patients have been randomised, and again after 50 % and 100 % of patient enrolment.. The clinician responsible for safety monitoring will receive additional information on demand, and can advise temporary or permanent stop in patient enrolment. He or she will have access to the randomisation code. The clinician responsible for safety monitoring is independent from the sponsor and will have no competing interest with regard to the study investigational products or study outcome.

# 9 Data management and monitoring

---

## 9.1 Case report forms (CRFs)

---

The designated investigator staff will enter the data required by the protocol into the case report form (CRF). The Principal Investigator is responsible for assuring that data entered into the CRF are complete, accurate, and that entry is performed in a timely manner. If any assessments are omitted, the reason for such omissions will be noted in the CRFs. Corrections, with the reason for the corrections will also be recorded. After database lock, the investigator will receive a digital copy of the subject data for archiving at the investigational site.

## 9.2 Source data

---

Data will be recorded directly into the CRF, which, along with the patients' medical record is to be considered the source data. Data important for patient safety and continued care must be duplicated in the patient's medical record as described below. Study-specific imaging data and blood analyses are independent source data.

The medical records of each patient should clearly describe at least:

- That the patient is participating in the study
- Date when the informed consent was obtained from the patient;
- Results of all assessments confirming a patient's eligibility for the study;
- Diseases (past and current; both the disease studied and others, as relevant);
- Surgical history, as relevant;
- Treatments withdrawn/withheld due to participation in the study;
- Results of assessments performed during the study;
- Treatments provided, changes in treatments during the study and the time points for the changes;
- Visits to the clinic / telephone contacts during the study, including those for study purposes only;
- Non-Serious Adverse Events and Serious Adverse Events (if any) including causality assessments;
- Date of, and reason for, discontinuation from study treatment;
- Date of, and reason for, withdrawal from study;
- Date of death and cause of death, if available.

## 9.3 Study monitoring

---

The investigator will be visited on a regular basis by the Clinical Study Monitor, who will check that the study is conducted as approved by the Ethics committee and adheres to GCP guidelines.

Sponsor's representatives (e.g. monitors, auditors) and/or competent authorities will be allowed access to source data for source data verification in which case a review of those parts of the hospital records relevant to the study may be required.

#### 9.4 Confidentiality

---

The investigator shall arrange for the secure retention of the patient identification and the code list. Patient files shall be kept for the maximum period of time permitted by each hospital. The study documentation (CRFs, Site File etc.) shall be retained and stored during the study and for 15 years after study closure. All information concerning the study will be stored in a safe place inaccessible to unauthorised personnel.

#### 9.5 Database management

---

Data will be entered into the CRF without delay and stored in a dedicated and secured area at OUS. Data will be stored in a de-identified manner, where each study participant is recognisable by his/her unique trial subject number. The data will be stored until Dec 31st 2034, or until the patient requires that his/her data are deleted. Data in the CRF will be handled according to GCP. Only the personnel authorised to enter and/or analyse data (i.e. investigators) will have access to the database.

#### 9.6 Biobanking

---

A biobank will be established at the Dept. of Cardiology, Oslo University Hospital, Rikshospitalet for the analysis of serum and plasma. The samples will be stored in multiple aliquots and labelled with the unique trial subject number, and the letter A signifying baseline, and the letter B signifying the end-of-study visit after 6 months. The samples will be stored at -80 degrees Celsius in a dedicated research freezer. The material is scheduled for destruction by Dec 31st 2034. [name] at Oslo University Hospital, Rikshospitalet will be responsible for the biobank.

## 10 Statistical methods and data analysis

---

### 10.1 Determination of sample size

---

This trial is designed to assess the effect of intravenous iron on peak oxygen consumption in heart transplant recipients with iron deficiency. We consider an increase in peak oxygen consumption of 1.5 ml/kg/min, equivalent to approximately half a Metabolic Equivalent of Task (MET), to represent a clinically meaningful improvement. An increase in O2 consumption of 1.5 ml/kg/min is approximately 6 % of the baseline maximal oxygen consumption in our heart transplant recipients. Data from the ACTION HF trial showed that a 6 % increase in peak oxygen consumption translated to an improved outcome in patients with heart failure. With a mean difference between the groups of 1.5 ml/kg/min and an expected repeat-measurement standard deviation of 2.5 ml/kg/min, a power of 80% and an  $\alpha$  of 5 %, we will need at least 44 patients in each group.

To allow for drop-out and to improve the chances of obtaining significance for secondary endpoints, we aim to include 100 patients.

### 10.2 Randomisation

---

#### 10.2.1 Allocation- sequence generation

---

Balanced, permuted block randomisation (in a 1:1: ratio for the two study arms) using random block sizes will be generated by the Research Support Unit at Oslo University Hospital using a computerised procedure. A complete, sealed randomisation list containing details of all patient

numbers and study group will be stored as essential documentation with the Trial Master File in a locked office.

#### **10.2.2 Allocation- procedure to randomise a patient**

---

We will use a computerised randomisation procedure for treatment allocation. Patient randomisation will be performed by random draw of sealed, opaque envelopes containing cards with the words “iron, 20 mg/kg” or “placebo (study drug no. ...)” once eligibility has been confirmed and the informed consent form has been signed. The study drug numbers will be assigned to each drug vial (or placebo card) by a nurse who does not participate in the trial or have competing interest regarding study outcome. This nurse will have exclusive access to the list linking study drug numbers, and batch numbers and expiry dates. According to the randomisation list, unique cards marked “iron, 20 mg/kg” or “placebo (study drug no. ...)” will be placed in sealed, opaque envelopes by a nurse not participating in the trial. A copy of the randomisation list will be stored in a sealed, opaque envelope in a locked cupboard along with the study drugs, a mechanism employed to minimise the possibility that those enrolling and assigning patients will obtain access to the list.

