### **5.6 Drug accountability**

---

The responsible site personnel will confirm receipt of study drug and will use the study drug only within the framework of this clinical study and in accordance with this protocol. The manufacturer (Pharmacosmos®) provides the active study drug. The study drug or matching placebo will be administered by trained hospital personnel. The manufacturer supplies study medication to the investigators on site. It will be labelled with information according to local regulation. The study medication will be stored in a locked refrigerator (2-8°C), protected from unintended use. All study medications supplied for this study must be retained in a safe place at all times of the study. Only personnel authorised by the principal investigator should dispense the study medication, and the accountability is the responsibility of investigator. A study medication inventory (dispensing records) for all medication dispensed must be maintained at all times. A unique, three-digit number will be assigned to each study drug dose (iron isomaltoside or placebo) by an independent nurse. The study drug number and drug dose (sham dose if placebo) will be available in the patient file. A list linking study drug numbers and batch-numbers and expiry dates will be kept in a sealed envelope in a locked closet, but can be opened if unblinding is necessary (see paragraph 10.2.3). The study drug inventory must contain information on Monofer® vial batch numbers and expiration dates. A study nurse will be responsible for drug storage, including keeping a temperature log, and the study drug inventory.

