## 5.8 Subject identification

Each study participant is identified by a unique subject number that is assigned after the subject signs the informed consent form. This number is generated through the randomisation process. Once assigned, the subject number cannot be reused for any other subject. The same primary identifier will be used throughout the study.

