5.4 Randomisation and Blinding

Balanced, permuted block randomisation (in a 1:1: ratio for the two study arms) using random block sizes was computed by the Research Support Unit at Oslo University Hospital. A complete, sealed randomisation list containing details of all patient numbers and study group is stored as essential documentation within the Trial Master File in a locked office. Treatment allocation is performed by random draw of sealed, opaque envelopes containing cards marked "iron isomaltoside 20 mg/kg" or "placebo". A nurse who does not participate in the trial or has competing interest regarding study outcomes prepared the envelopes and has exclusive access to the list linking study drug numbers, and batch numbers and expiry dates. The administration of the study drug is performed by nurses who are not part of the study team. The study participants (patients) and all study personnel, including investigators, personnel assessing outcomes, study nurses, data analysts and treating physicians and nurses, are blinded to allocation to study drug.

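### The plan specifies a permuted-block list but allocates by random draw of envelopes with no stated opening order, which, read literally, discards the blocks

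*Protocol*

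**What the plan says.** On generating the sequence, Protocol 10.2.1 states: "Balanced, permuted block randomisation (in a 1:1: ratio for the two study arms) using random block sizes will be generated" by the hospital's research support unit. SAP 5.4 agrees that a list "using random block sizes was computed by the Research Support Unit". The list holds patient numbers with their study group and is kept sealed.

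On allocating a patient, Protocol 10.2.2 opens with "We will use a computerised randomisation procedure for treatment allocation". It continues: "Patient randomisation will be performed by random draw of sealed, opaque envelopes containing cards with the words" for one arm or the other, once eligibility and consent are in place. The cards follow the list ("According to the randomisation list, unique cards marked" for iron or placebo go into the envelopes). SAP 5.4 describes the same step: "Treatment allocation is performed by random draw of sealed, opaque envelopes containing cards marked" with the treatment.

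Two kinds of number are described. Protocol 5.6 numbers the doses: "A unique, three-digit number will be assigned to each study drug dose (iron isomaltoside or placebo) by an independent nurse". Protocol 5.8 says of the subject number: "This number is generated through the randomisation process". Neither is tied to an envelope's place on the list.

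**The concern.** A permuted-block list constrains the allocation only if it is used in order. If the envelopes are filled from the list and then drawn at random, only the total of each arm in the pool stays fixed, and the block order has no effect.

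Three things are at stake:

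- **Balance** during recruitment, and at the end if recruitment stops early or if more envelopes were prepared than patients enrolled. Protocol 6.4.2 lists recruitment difficulty among the reasons to stop.
- **A documented order** in which a skipped or redrawn envelope would show. This matters in a single-site trial with manually handled envelopes.
- **Accurate reporting.** A report that calls the method permuted-block would be wrong if the draw was free.

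The opening sentence of Protocol 10.2.2 adds some doubt, because it does not say whether the computer generates the list or assigns the patient.

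**Working it through.** **Inputs from the documents.** Difference 1.5 ml/kg/min, SD 2.5 ml/kg/min, 80% power, 44 per group, 100 to be enrolled (Protocol 10.1); two-sided 5% (Protocol 10.5); safety reports after 20 patients and at 50% and 100% of enrolment (Protocol 8.6).

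**Assumptions.** The documents give neither the number of envelopes nor the block sizes. I take a pool of 50+50, with 60+60 as a sensitivity case, and largest blocks of 4 to 10.

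**1. The plan's own figure.** n per group = 2 × (1.960 + 0.842)² × (2.5/1.5)² = 43.6, rounded up to 44. This reproduces the stated 44. Exact t-test power at 44 per group is 79.5%.

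**2. Literal random draw.** With N envelopes, half per arm, the number drawn to one arm after n patients is hypergeometric. The arm-size difference D has mean 0 and

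SD(D) = √[n(N − n)/(N − 1)].

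For N = 100 and n = 20: √(20 × 80/99) = 4.02. For N = 100 and n = 50: √(50 × 50/99) = 5.03. For N = 120 and n = 100: √(100 × 20/119) = 4.10.

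| Patients | SD(D), 50+50 | P(difference ≥ 6), 50+50 | SD(D), 60+60 | P(difference ≥ 6), 60+60 |
|---|---|---|---|---|
| 20 | 4.02 | 21.1% | 4.10 | 22.0% |
| 50 | 5.03 | 31.7% | 5.42 | 35.5% |
| 100 | 0 | 0 | 4.10 | 22.0% |

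If enrolment ended at 88 from a 50+50 pool, the SD would be √(88 × 12/99) = 3.27 and P(difference ≥ 6) 12.1%.

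**3. Same list, opened in order.** Each completed block contributes a difference of zero, and an open block of size b contributes at most b/2. The cap at any time is therefore 2, 3, 4 or 5 for largest blocks of 4, 6, 8 or 10. In 40,000 simulated lists with sizes drawn from {4,6}, {4,6,8} or {6,8,10}, the SD was 0.95 to 1.25 at 20, 50 and 88 patients, and a difference of 6 or more never occurred.

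**4. Effect on power.** Two-sided t-test, noncentral t, standardised difference 1.5/2.5 = 0.6, for a difference of 6 between arms:

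| Total | Equal arms | Arms differing by 6 |
|---|---|---|
| 88 | 44 v 44: 79.5% | 41 v 47: 79.3% |
| 50 | 25 v 25: 54.7% | 22 v 28: 54.1% |

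**5. Can the allocations be traced to the list?** The dose number shows what was given. The subject number comes out of randomisation, but the documents do not say whether it is fixed to an envelope beforehand. Whether the allocations follow the filed list therefore cannot be judged from the documents.

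**The case against.** The strongest reply is that random draw is loose wording for opening the next concealed envelope. The list pairs patient numbers with groups and the cards are prepared from it, and both would serve little purpose if the envelopes were then mixed. This may well be what was intended. But both documents use the phrase and no other sentence supplies an order. A draw restricted to the current block's envelopes would also keep the blocks, and that is not stated either.

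The second reply is that little follows. This largely stands. A concealed draw from a 1:1 pool is unbiased, the split is exactly equal once a 50+50 pool is used up, and the loss of power is under one percentage point. The primary ANCOVA (SAP 9.1) does not depend on the blocks, and no interim efficacy analysis is planned. The imbalance at 100 patients appears only in the 60+60 case, and the documents mention no spare envelopes. An early stop for recruitment is not obviously likely: about 500 recipients in follow-up (Protocol 4.1) at 48% iron deficiency (Protocol 1) gives about 240 before exclusions and refusals.

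The third reply is that allocations do leave a record through unique cards, numbered doses, the patient file and the sealed list. That is true of the treatment each patient received. It does not establish the order in which envelopes were opened. An opening log may exist in site procedures, but the documents do not mention one.

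The point about the computerised sentence is minor, since Protocol 10.2.1 already says the list is generated by computer.

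**Conclusion.** The concern holds. The allocation step as written does not deliver the block property that both documents claim, and nothing elsewhere in them supplies the missing order. If the draw is literal, differences of 6 or more between arms have a probability of about 21 to 22% after 20 patients and 32 to 35% after 50. List order would hold the difference to 2 to 5 for largest blocks of 4 to 10. These figures rest on the assumed pool and block sizes. Validity is not in question and power is essentially unchanged. The case for acting is a contradiction on a basic reporting item, the missing check on envelope order, and balance if enrolment ends early. The correction should be made, though its numerical effect is modest. Confidence is medium, because the wording may simply be loose.

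**What to change.** In Protocol 10.2.2 and SAP 5.4, replace the random draw with an explicit rule:

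- Envelopes are numbered sequentially in the order of the block list.
- Once eligibility is confirmed and consent signed, the next number in order is opened.
- Envelope number, subject number, date and time are logged and reconciled to the list.

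Reword the first sentence of Protocol 10.2.2 to say that the list is computer-generated and that allocation is by envelope.

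SAP 5.4 describes the list and envelopes as already prepared, so draws may have been made. If any were free draws, describe the method for those patients as a draw without replacement from a 1:1 pool, state the pool size, document the actual allocations, and drop the permuted-block label for them.

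The cost is a wording change, numbering any unused envelopes and one log line per patient, with no extra staff or patients. If every envelope has been used, only the description changes.
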